1.1 Synopsis

Future Health Today (FHT) is a stratified head-to-head cluster randomised controlled trial (RCT) of quality improvement (QI) activities in general practice in Australia. The QI program that forms the intervention consists of a new technology platform (FHT, with audit, recall, clinical decision support and monitoring of QI activity capability) and case-based learning series for specific clinical areas. For the FHT trial we have focused on QI programs for two common conditions managed in general practice, chronic kidney disease (CKD) and cancer-risk. The QI CKD program focuses on reducing cardiovascular disease (CVD) risk for individuals with a recorded diagnosis or pathology results consistent with a diagnosis of CKD. The QI cancer-risk program focuses on the appropriate investigation and follow-up of people at increased risk of an undiagnosed cancer among general practice patients. General practices will be randomly assigned equally to either the QI CKD program or the QI cancer-risk program, with different target populations and outcomes measured for each QI program. Thus, practices randomised to the QI cancer-risk program will act as an active control for the QI CKD program, and vice versa.

This Statistical Analysis Plan (SAP) will focus on the CKD intervention and a separate SAP will be developed documenting the statistical analysis for the cancer-risk intervention. The analysis and findings for each study (CKD and cancer-risk) will be published as separate manuscripts following the CONSORT (Consolidated Standards of Reporting Trials) guidelines.¹ The background and rationale for the FHT trial are described in the trial protocol, including the setting, recruitment, eligibility criteria, randomisation, and sample size calculations. This document elaborates on the statistical analysis for the primary and secondary outcomes of the CKD intervention, including sensitivity and pre-planned explanatory analyses, non-adherence adjusted analyses, and handling of missing outcome data where appropriate. This SAP also describes the analysis for the immediate outcomes for the health economic evaluation related to costs of the intervention and health services utilisation. Whereas the study trial protocol describes the simulation study investigating the longer-term health economics impacts of implementing FHT QI program on the incidence of CVD and renal replacement events in patients with CKD. The process evaluation to identify the barriers and facilitators to successful implementation of FHT in daily practice will be described in a separate document.

1.2 Primary Hypothesis

The null hypothesis is that there is no difference in the proportion of patients with a recorded diagnosis or pathology results consistent with a diagnosis of CKD who attend general practice participating in FHT CKD QI program (intervention arm) who receive guideline concordant care to reduce CVD risk, within the 12 months period post-randomisation, compared with patients attending general practice providing usual care for CKD (active control arm). The alternative hypothesis is that there is a difference.

1.3 Study Aims/Objectives

The primary objective of the CKD trial component is to determine the effectiveness of the FHT QI program for CKD compared to usual care for patients with a recorded diagnosis or pathology results consistent with a diagnosis of CKD receive guideline concordant care²⁻⁴ within 12-months post-randomisation to reduce CVD risk.

The secondary objectives of the trial are to determine the effectiveness of FHT QI program for CKD compared to usual care for patients with a recorded diagnosis or pathology results consistent with a diagnosis of CKD regarding the:

- a) proportion of patients that are prescribed an angiotensin-converting enzyme inhibitor (ACEI) or angiotensin receptor blockers (ARB) consistent with guidelines to reduce CVD risk²⁻⁴, prescribed during the 12-month follow-up period post-randomisation.
- b) proportion of patients who are prescribed statins consistent with guidelines to reduce CVD risk^{4,5}, prescribed during the 12-month follow-up period post-randomisation.
- c) mean systolic blood pressure (mmHg) using the most recent recorded reading at 12-months post-randomisation
- d) mean lipid results (total cholesterol, low-density lipoprotein (LDL) cholesterol, high-density lipoprotein (HDL) cholesterol and triglycerides all mmol/L) using the most recent recorded results at 12-months post-randomisation
- e) mean urine albumin:creatinine ratio (uACR) based on most recently recorded results at 12months post-randomisation
- f) proportion of patients with a reduction in uACR of at least 30% from baseline measurement
- g) proportion of patients classified as being at low, moderate, or high cardiovascular disease risk at 12-months post-randomisation
- h) mean eGFR (ml/min/1.73²) between baseline at 12-months post-randomisation
- i) rate of general practice encounters per patient over the 12 months post-randomisation.

For the health economics analysis, the aim is to quantify the costs of the delivery of the FHT QI program and the health care service costs. Specifically, the objectives are:

- j) to estimate the cost of the FHT software program installation for QI and cost of training for general practitioners to use the software
- k) to examine the primary health service utilisation and cost incurred by patients in the intervention arm compared to control arm over the 12-month period post-randomisation.

2. Trial Design

The FHT trial is a stratified head-to-head cluster randomised controlled trial. The unit of randomisation is the general practice, where practices are randomly allocated concurrently on 1:1 ratio to either participate in the FHT CKD QI module (intervention arm) or the FHT Cancer-risk module (active control arm for the CKD study). All general practices will be provided access to the respective QI programs at the commencement of the trial (October 4th, 2021). Please refer to the trial protocol for a detailed description of the intervention and comparator.

2.1 Study population

The trial will be conducted in general practices in Victoria and Tasmania. Full details of the eligibility and exclusion criteria for general practices are provided in the trial protocol.

Patients attending general are eligible if at the commencement of the trial (4th of October 2021) they:

- Are aged 18-80 years (inclusive)
- Have a recorded diagnosis of CKD or pathology results consistent with CKD⁶ and that may benefit from pharmacological therapy to reduce CVD risk consistent with Kidney Health Australia³, RACGP Red Book² and National Vascular Disease Prevention Alliance Guidelines⁴

Eligible patients will be excluded if they:

- Have a recorded history of renal transplant or chronic dialysis
- Are pregnant
- Are recorded as no longer active in the general practice or deceased in the EMR

2.2 Framework

The framework for the statistical analysis will utilise a superiority framework.

2.3 Interim Analyses and Stopping Guidelines

No formal interim statistical analyses are planned for this trial. As the data used in the study is EMR data extracted from general practices, no formal data monitoring and no stopping guidelines were required.

2.4 Data Management and Workflow

General practice and practice staff characteristics will be collected via survey before randomisation.

Patient characteristics, baseline measures and outcome data will be measured using patient data extracted from general practice EMRs and stored in the Patron database. Patient data will be extracted from each practice using the GHRANITE tool at each data collection period namely, 4th October 2021 (baseline), 4th April 2022 (6 months), 4th July 2022 (9 months) and 30th September 2022 (12 months). The extracted data will be processed and curated by Patron data team members and stored within the Patron enclave using a separate database for each data collection period. This process takes at least two weeks.

The FHT QI module installed within practices as part of the FHT intervention interacts with the practice EMR system, running the FHT algorithms over patient data to identify patients with CKD or pathology consistent with CKD who could benefit from initiation of statins and/or ACEI/ARBs. The criteria used to identify the eligible patients with a recorded diagnosis or pathology results consistent with a diagnosis of CKD who attend general practice and the creation of the recommendations for guideline concordant care to consider (flags) are outlined in the Future Health Today business requirements document which was used to develop the FHT algorithms embedded in the technology platform. Within participating general practices individual patient level recommendations can be viewed. However, only aggregate level data is extracted by Future Health Today platform and available to the research team. As a result, these data are not linked with Patron database used for the trial statistical analysis.

Therefore, part of this curation process is the replication of the eligible patients and flags generated by FHT algorithms in the practices, patient outcomes and baseline measures, using identical algorithms to those embedded within, and executed by, FHT platform within the Patron dataset. These algorithms were independently validated by the biostatistician using baseline data. Limitation of this approach is that we will only be able to derive the action taken by clinicians if they were recorded in an extractable field in the EMR that is included in the Patron dataset, such as, medication prescriptions ordered, pathology results and observations.

All data within the Patron enclave is deidentified with patient and practice identifiers replaced by a unique hashed code prior to the data leaving the general practice. Data managers and analysts can access the databases for the project and utilise Structured Query Language (SQL) queries to create Comma Separated Values (CSV) files containing the data required for the trial analysis. Files downloaded from the Patron databases will be saved within a secure virtual machine accessible only by the study biostatisticians, health economists and the data manager. The virtual machine requires multifactor authentication to access. Within the secure virtual environment, the data manager or biostatistical will then import the CSV data files into Stata Statistical Software v17⁷ for data processing and statistical analysis. Data will be checked for errors, resolving them where possible. Labelling, recoding, and the creation of composite variables will be carried out, where required. Data from each data collection period will be collated using the unique patient identifier.

The statistical analysis for the CKD study will be conducted by the biostatistician, with oversight from the senior biostatistician. The senior biostatistician will review the statistical analyses and will explicitly check the Stata programming code for the statistical analysis, reporting and interpretation of the results. Health economists will be responsible for the analyses related to the health economics component of the trial. The files for the final analysis will be stored within the secure virtual environment, as well as all subsequent outputs including (but not limited to) Stata Statistical software Do files (*.do), data sets (*.dta), log (*.log) and graph (*.gph) files.

The biostatistician conducting the analysis and study investigators not involved in practice support and engagement will remain masked to the allocation of practices. Masking will be maintained as general practices are de-identified by the GRHANITE data extraction tool and assigns a unique code to the general practice records and patient codes. The study arm codes made available to the biostatistician conducting the analysis will be uninformative. The results for the primary outcome for the CKD study will initially be presented to the FHT investigators using the uninformative study code to maintain masking and will be revealed after the results have been interpreted.

2.5 Timing of final analysis and outcomes assessment

Statistical analyses for the CKD study are planned to commence when the final data set is received late October 2022 and after the Statistical Analysis Plan has been uploaded to the Australian and New Zealand Clinical Trials Registry. Analysis for the cancer-risk study described in a separate SAP is planned to commence in 2023.

Primary and secondary outcomes will be assessed at the trial end date, 30th September 2022, approximately 12-months after the trial start date, 4th October 2021. Subsequent references to the trial period refer to this 12-month period. The outcomes at end of the trial will be based on their most recent

recorded medication prescribed, observations and/or pathology test results in the EMR within the trial period.

Baseline measures of the outcome and patient characteristics will be assessed at the trial start date (4th October 2021). The baseline measures of the outcomes for eligible patients will be based on the history of observations and/or pathology test results in the EMR in the preceding 12 months from the 4th of October 2021, except for systolic blood pressure which will be based on the preceding 6 months, and current medication status, which considers the entire history of prescribed medications.

3. Statistical Principles

3.1 Level of statistical significance and confidence intervals

Estimates of the intervention effect will be reported with 95% confidence intervals and two sided-p-values.

3.2 Adjustment for multiple tests including description of controlling for type I error

No adjustments will be made for multiplicity. Separate sample sizes were determined for the respective primary outcomes for the CKD and cancer-risk studies and different samples will be drawn from the respective populations for the two studies. The total number of practices recruited in the trial were based on the sample size required for the CKD arm of the trial.

3.3 Adherence and protocol deviations

Protocol deviations include technical issues resulting in FHT being inaccessible for periods throughout the trial and preventing the extraction of data to the Patron system. Technical issues with FHT, practice computers/servers (preventing upload of data or function of FHT) or other technical issues that prevent staff from accessing FHT could negatively impact on the ability of GPs to participate in quality improvement program and to receive recommendations to facilitate delivery of guideline concordant care to patients within their cohort and may attenuate the effect of the intervention. Practices allocated to the active control arm will only have access the QI cancer-risk program.

4. Trial Population and Statistical Analysis

4.1 Outcomes

The **primary outcome** is the proportion of eligible patients with a diagnosis or pathology results consistent with CKD at baseline subsequently prescribed ACEI/ARB, or/and statins consistent with Kidney Health Australia³, RACGP Red Book² and National Vascular Disease Prevention Alliance Guidelines⁴ within the 12 months trial period , and will be considered to have received guideline concordant care. The absence of any recorded prescription for an ACEI/ARB and/or statins during the trial period will be considered equivalent to the patient not being prescribed the medications.

Secondary outcomes will include the individual indicators for guideline concordant care, including recorded medication prescribed, observations and/or pathology test results and number of encounters of patients that attended during the 12-month trial period.

(1) The proportion of eligible patients with a diagnosis or pathology results consistent with CKD at baseline subsequently prescribed ACEIs or ARBs consistent with Kidney Health Australia³, RACGP Red Book² and National Vascular Disease Prevention Alliance Guidelines⁴ within the 12 month trial period. The absence of any recorded prescription for an ACEI/ARB during the trial period will be considered equivalent to the patient not being prescribed an ACEI or ARB.

(2) The proportion of eligible patients with a diagnosis or pathology results consistent with CKD at baseline subsequently prescribed statins consistent with the National Vascular Disease Prevention Alliance Guidelines⁴ and ACC/AHA Guideline on the Primary Prevention of Cardiovascular Disease⁵ within the 12 month trial period. The absence of any recorded prescription for a statin will be considered equivalent to the patient not being prescribed a statin.

(3) Change in mean systolic blood pressure (mmHg) between baseline and the end of the trial. Patients' most recent systolic blood pressure measurement at baseline, up to six-months pre-trial (4th April 2021) from the trial start date will be compared to the most recently recorded measurement occurring within the trial period at the end of the trial. The timing of blood pressure measurements may vary within and between study arms.

(4) Change in mean lipid results (mmol/L) between baseline and the end of the trial. Patients' most recent lipid measurement at baseline, up to 12-months pre-trial (4th October 2020) will be compared to the most recently recorded measurement occurring within the trial period, at the end of the trial. The timing of lipid measurements may vary within and between study arms. Four types of lipids will be investigated:

- Total cholesterol
- LDL cholesterol
- HDL cholesterol
- Triglycerides

(5) Change in mean uACR between baseline and the end of the trial. Patients' most recent uACR measurement at baseline ($uACR_{baseline}$), up to 12 months before the trial start date (4th October 2020) will be compared to the most recently recorded measurement occurring within the trial period ($uACR_{12mth}$), at the end of the trial. The timing of uACR measurements may vary within and between study arms.

(6) The proportion of eligible patients whose uACR decreases by \geq 30%, defined as follows:

$$\frac{(uACR_{baseline} - uACR_{12mth})}{uACR_{baseline}} \ge 0.3$$

(7) The proportion of patients categorised as low (<10%), moderate (10 to 15%), and high risk (>15%) of CVD within the next 5-years based on the Framingham Risk Equation used by the Australian

management guidelines⁴. Patients will automatically be classified as being at high risk of CVD regardless of their Framingham 5-year risk if they have at least one of the following clinically conditions:

- Diabetes and age > 60 years
- Diabetes with microalbuminuria (> 20 mcg/min or uACR > 2.5 mg/mmol for males, > 3.5 mg/mmol for females)
- Moderate or severe chronic kidney disease (persistent proteinuria or eGFR< 45 mL/min/1.73 m2)
- A previous diagnosis of familial hypercholesterolaemia
- Systolic blood pressure \geq 180 mmHg or diastolic blood pressure \geq 110 mmHg
- Serum total cholesterol > 7.5 mmol

(8) The change in mean eGFR (ml/min/1.73²) between baseline and the end of the trial. Patients' most recent eGFR measurement at baseline, up to 12 months prior to the beginning of the trial (4th October 2021) will be compared to the most recently recorded eGFR measurement occurring within the trial period, at the end of the trial. The timing of eGFR measurements may vary within and between study arms.

(9) The rate of general practice encounters per patient over the trial period. This will be calculated using total number of general practice encounters in the 12-month trial period of all eligible patients with a diagnosis or pathology results consistent with CKD at baseline divided by the total time they were observed in the trial. For each patient, time will be one year, calculated from the date the trial commenced (4th October 2021) to the end of the trial (30th September 2022), except for patients/practices that discontinued during the trial period, where time observed will be calculated from the 4th October 2021 to the date the patient(s) discontinued/withdrew.

Health economics outcomes are:

(10) The cost of the installation for the software program for QI, training, QI support and education. This will be calculated at the general practice level, using cost data collected by Health and Biomedical Informatics Centre (HABIC R²) who developed and provided technical support for the FHT software and the FHT investigators and research team who liaised with practices and facilitated the education sessions.

(11) Cost of primary care service utilisation per patient per year. These will be calculated based on Medicare items, Provider Charge, Schedule Fee, Patient Out of Pocket in the Medicare Benefits Schedule (MBS) data linked to patients in the Patron for the FHT evaluation.

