4.2 Baseline practice, practice staff, and patient characteristics

Baseline practice and practice staff characteristics include:

- State (Victoria, Tasmania)
- IRSD terciles based on the Index of Relative Socio-Economic Disadvantage (IRSD) ⁸ using the practice postcode. The first tercile represents relatively disadvantaged sociodemographic geographic areas compared to geographic areas with higher ranks (Tercile 3).
- Practice participation in a formalised QI program in the past 6 months (yes, no)

- Practice size based on the GP full-time equivalent (FTE) of 4 or less FTE or greater than 4 FTE as reported by the practice. FTE will be defined as the total number of full-time GPs plus the total number of part time GPs multiplied by 0.5FTE.
- GPs sex (male, female)
- GPs age group (<35 years; 35 to 50 years; >50 years)
- Number of FTE registered nurses. FTE will be defined as the total number of full-time nurses plus the total number of part time nurses multiplied by 0.5FTE.
- Registered nurses' sex (male, female)
- Registered nurses age group (<35 years; 35 to 50 years; >50 years)
- Number of FTE practice managers and administrative staff. FTE will be defined as the total number of full-time practice managers/administrative staff plus the total number of part time practice managers/administrative staff multiplied by 0.5FTE.
- Practice managers/administrative staff sex (male, female)
- Practice managers/administrative staff age group (<35 years; 35 to 50 years; >50 years)

Patient characteristics and medication prescribed, observations and/or pathology test results recorded at baseline (4th October 2021) extracted from the EMR include:

- Sex (male, female, other)
- Age (years)
- ACEI/ARB prescription status (ACEI only, ARB only, both ACEI/ARB, None)
- Statin prescription status (yes/no)
- Recommendation for guideline concordant care to consider initiating medications (Statin only; ACEI/ARB only; Both statin and ACEI/ARB)
- Systolic blood pressure (mmHg)
- Total cholesterol (mmol/L)
- LDL cholesterol (mmol/L)
- HDL cholesterol (mmol/L)
- Triglycerides (mmol/L)
- uACR (mg/g)
- eGFR (ml/min/1.73²)
- CVD risk category (low, medium, and high)
- Recorded diagnosis of type 2 diabetes prior to baseline (yes/no)

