4.6.2 Secondary outcomes

Statistical methods described for the primary outcome will be used for the **binary secondary outcomes 1, 2, and 6.** For each outcome, an additional covariate will be fitted in the regression model. For outcome 1, we will adjust for whether a recommendation would have been made to consider initiating ACEIs or ARBs for the patient (yes/no). Similarly for outcome 2, we will adjust for whether the recommendation would have been received to consider initiating statins (yes/no). For outcome 6, we will include uACR at baseline as a covariate.

For the analysis of continuous secondary **outcomes 3, 4, 5 and 8**, a mixed effects linear model with study arm, baseline measure of the outcome (where appropriate), randomisation stratification factors (GP FTE and IRSD terciles) will be fitted as fixed effects and general practice as a random effect. The estimated intervention effects will be reported as the difference in means between the intervention and active control arms with 95% confidence intervals and p-values.

Outcomes with a skewed distribution may be log-transformed, in which case, the estimated intervention effect will be reported as a ratio of the geometric means between study arms, with their respective 95% confidence interval and p-value.

Secondary outcome 7 will be analysed using the proportional odds logistic regression model with randomisation stratification factors (GP FTE and IRSD terciles) and baseline CVD risk group included as fixed effects. Generalised Estimating Equations with an exchangeable correlation structure and robust standard errors will be used to allow for correlation of outcomes within general practice. An alternative model will be considered if the assumption of proportional odds is not met.¹¹

The estimated intervention effect will be reported as a cumulative odds ratio with their respective 95% confidence interval and p-value.

Secondary outcome 9 will utilise a Poisson mixed effects model (or a Negative Binomial mixed effects model if overdispersion is detected), with fixed effects for study arm and the randomisation stratification factors (GP FTE and IRSD terciles), and random effect for general practice. The estimated intervention effect will be reported as differences in rate between the intervention and control arms and rate ratios with 95% confidence intervals and p-values.

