4.7.3 Subgroup Analysis

Three sub-group analyses will be conducted, regardless of the trial findings of the primary analyses.

- Patients that had a recommendation to consider initiation of a statin may have been prescribed ACEI/ARB or did not require this class of medications at baseline. Thus, we will conduct a subgroup analysis using the same regression models described above for the secondary outcomes 1, 5 and 6 by whether patients receive a recommendation to consider initiation of ACEIs/ARBs at baseline. For patients that receive a recommendation to consider initiation of ACEIs/ARBs at baseline and receive a prescription for the class of medications during the trial period, we will investigate the effect of the time between receiving their first prescription to the most recent measure of the pathology measure at the end of the trial period (<3 months; >=3-6 months; >=6 months) for the secondary outcomes 5 and 6, as appropriate. These findings may be reported in part with the primary analysis or in a separate publication.
- 2. Patients that had a recommendation to consider initiation of an ACEI/ARB may have been prescribed statins or may not require statins at baseline. Thus, we will conduct a sub-group analysis using the same regression models described above for the secondary outcome 2 and 4 by whether patients would receive a recommendation to consider initiation of statins at baseline. For patients that receive a recommendation to consider initiation of statins and

receive a prescription for statin during the trial period, we will investigate the effect of the time between receiving their first statin prescription to the most recent measure of the pathology measure at the end of the trial period (<3 months; >=3-6 months; >=6 months) for outcome 4, as appropriate. These findings may be reported in part with the primary analysis or in a separate publication.

3. The statistical analyses described for the primary and secondary outcomes will be repeated for eligible patients with and without a recorded diagnosis of type 2 diabetes at baseline. This subgroup analysis will be reported in a separate paper to the primary analysis.

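### The CKD primary outcome is not tied to the class flagged for initiation, so a repeat script for a class already taken counts as guideline concordant care and pulls the risk difference toward zero

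*SAP*

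**What the plan says.** All references are to the CKD SAP.

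- **Target of the program (section 2.4).** The algorithms run in the practice to "identify patients with CKD or pathology consistent with CKD who could benefit from initiation of statins and/or ACEI/ARBs".
- **Eligibility (section 2.1).** Patients have CKD "that may benefit from pharmacological therapy to reduce CVD risk consistent with Kidney Health Australia" and two other guidelines. They need not be untreated with both classes.
- **Baseline flag (section 4.2).** The recorded variable is "Recommendation for guideline concordant care to consider initiating medications (Statin only; ACEI/ARB only; Both statin and ACEI/ARB". There is no category for no recommendation, here or in Appendix B Table 2.
- **Overlap (section 4.7.3).** On those flagged for a statin, the text reads: "recommendation to consider initiation of a statin may have been prescribed ACEI/ARB or did not require this class of medications at baseline". The mirror statement is made for patients flagged for an ACEI/ARB, who may already be on a statin.
- **Primary event (section 4.1).** It counts those having a "diagnosis or pathology results consistent with CKD at baseline subsequently prescribed ACEI/ARB, or/and statins consistent with Kidney Health Australia" and two other guidelines. The non-event is defined by "The absence of any recorded prescription for an ACEI/ARB and/or statins during the trial period".
- **Primary model (section 4.6.1).** The covariates are the stratification factors only, GP FTE and IRSD terciles.
- **Secondary outcomes 1 and 2 (section 4.6.2).** "For outcome 1, we will adjust for whether a recommendation would have been made to consider initiating ACEIs or ARBs for the patient (yes/no"), with the statin flag used in the same way for outcome 2.
- **Flag subgroups (section 4.7.3).** These cover outcomes 1, 5 and 6 (ACEI/ARB flag) and 2 and 4 (statin flag). The primary outcome is not among them.

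**The concern.** The program asks the GP to start a named class. The primary event asks only whether either class was prescribed during the year. The two part company for a patient flagged for a statin who is already on an ACEI/ARB, or the reverse. If the GP repeats the existing drug and does nothing about the flag, the patient is scored as having received guideline concordant care, although the plan's own algorithm would still show the recommendation as unanswered.

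Such patients succeed at a high rate in both arms for reasons unrelated to the program. They raise both proportions, shrink the risk difference and the odds ratio, and overstate how much of the recommended care was delivered.

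**Working it through.** **Step 1: who is affected.** Take a flag to mean that the class is not currently prescribed.

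- Flagged for both classes: nothing to repeat.
- Flagged for one class, other class not needed: nothing to repeat.
- Flagged for one class, already on the other: a repeat script meets the event.

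Only the third group matters. Section 4.7.3 says that it may occur but does not give its size.

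**Step 2: do the words about consistency with guidelines already restrict the event to the flagged class?** Secondary outcome 1 uses the same phrase and the same guidelines as the primary outcome. Section 4.6.2 fits the ACEI/ARB flag as a yes/no covariate for it, and section 4.7.3 estimates its effect within each flag level. If only flagged classes could score, every patient at the 'no' level would be a certain failure: the covariate would separate perfectly and no effect could be estimated there. Those analyses work only if unflagged patients can score.

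**Step 3: size.** The SAP states no sample size, event rate or power, so there is no figure to reproduce. Let

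- s = share of eligible patients flagged for one class and already on the other;
- r = their chance of a repeat script in the trial period, equal in both arms;
- p0, p1 = initiation rates of a flagged class in the control and intervention arms, independent of repeat scripts.

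Composite rate = s*(r + (1 - r)*p) + (1 - s)*p = s*r + (1 - s*r)*p.

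Risk difference = (1 - s*r)*(p1 - p0).

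The factor (1 - s*r) does not depend on the initiation rates. All inputs below are assumptions. With p0 = 10%, p1 = 20% and r = 0.9:

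| s | s*r | Control | Intervention | Difference (points) | Odds ratio | Share kept |
|---|---|---|---|---|---|---|
| 0 | 0 | 10.0% | 20.0% | 10.0 | 2.25 | 100% |
| 0.10 | 0.09 | 18.1% | 27.2% | 9.1 | 1.69 | 91% |
| 0.25 | 0.225 | 30.25% | 38.0% | 7.75 | 1.41 | 77.5% |
| 0.50 | 0.45 | 50.5% | 56.0% | 5.5 | 1.25 | 55% |
| 0.75 | 0.675 | 70.75% | 74.0% | 3.25 | 1.18 | 32.5% |

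Worked row, s = 0.50: control 0.45 + 0.55*0.10 = 0.505; intervention 0.45 + 0.55*0.20 = 0.560; difference 0.055.

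With r = 0.7 the share kept at s = 0.10, 0.25, 0.50 and 0.75 is 93%, 82.5%, 65% and 47.5%. With 20% against 30% initiation, r = 0.9 and s = 0.50, the rates are 56.0% and 61.5%: again 5.5 of 10 points.

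**Step 4: does anything downstream correct it?** The primary model has no term for flag or baseline treatment, and the flag subgroups leave the primary outcome out. The tabulation of baseline flag and treatment by arm shows the mix but does not change the estimate.

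**The case against.** The strongest reply is that this is an ambiguity. The SAP uses the term guideline concordant care for the flags themselves, and section 2.4 says that patient outcomes are replicated in Patron with the same algorithms as the platform, specified in a document that is not shown. A flag-based derivation might therefore be intended. That cannot be excluded as an intention, but the text does not say it, and Step 2 shows that the same phrase cannot carry that meaning for outcome 1. Either way the event needs to be written down.

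Other parts of the reply stand:

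- **Size.** A reader might infer that repeat scripts swamp the effect. The SAP does not support this: s, r and the initiation rates are all unknown, and at s = 0.10 over 90% of the difference is kept.
- **Power.** A reader might also infer a specific loss of power. That would require the trial to have been sized on initiation of the flagged class. The sizing is in the protocol, and if it used the composite rate the loss would not arise in that form. A figure would also need an assumption about the ICC of the redefined event.
- **Outcomes 1 and 2.** Their 'no' level does mix patients already treated with patients not needing the class. But section 4.7.3 already plans the effect by flag, with estimates, confidence intervals and an interaction test for each subgroup. Which set is called the main one is largely a matter of presentation.
- **Direction.** With r equal in both arms, the dilution is toward no difference and cannot create a false benefit.

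**Conclusion.** The point holds for the primary outcome. As worded, the event can be met by a repeat script for a class that the patient was not flagged to start, and neither the primary model nor the planned subgroups correct for it. The risk difference is multiplied by (1 - s*r). Over s = 0.10 to 0.75, the share kept runs from 91% to 32.5% at r = 0.9 and from 93% to 47.5% at r = 0.7. This rests on r being equal in both arms, on repeat scripts and initiation being independent, and on a flag meaning that the class is not currently prescribed. The position of this trial within the range cannot be told from the SAP, and no statement about power is justified. The problem is confined to patients flagged for one class and already on the other. It does not require a new main analysis set for outcomes 1 and 2.

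**What to change.** Before unmasking, revise sections 4.1 and 4.6.1 of the CKD SAP:

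1. Define success as at least one prescription, from 4 October 2021 to 30 September 2022, of a class for which the replicated algorithm flagged the patient at baseline. When both classes are flagged, either suffices, in line with the existing or/and wording.
2. State that prescriptions of an unflagged class do not count.
3. Add baseline flag category (statin only, ACEI/ARB only, both) as a covariate in the primary model. The fallback already given for a risk-difference model that fails to converge still applies.
4. Keep the any-prescription version as a supportive analysis.

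Cost: wording, one derived variable and one covariate; flags and prescriptions are already in Patron. The stated success proportions will be lower. The redefined event must also be checked against the protocol's sample-size assumption, because section 3.2 bases the number of practices on the CKD calculation. If the arm codes have already been revealed, the flagged-class version should be reported as post hoc, as section 4.8 requires.
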